#### 10. STATISTICS AND DATA ANALYSIS

### 10.1 Sampling

All pregnant patients attending Liverpool Women's Hospital Trust (diabetes antenatal clinic, fetal medicine unit growth clinic, maternity assessment unit with reduced fetal movements, admitted in antenatal ward with reduced fetal movements) will be considered to take part in this study.

As this is an exploratory study and no hypothesis testing is planned a formal sample size calculation has not been performed.

We will aim to include 60 patients per cohort. There will be three cohorts, so the total number of patients will be 180, and the number of scans performed 360. The sample size estimation was determined by the study team including the statistician because this is an exploratory study with a binary primary outcome (acceptable vs non-acceptable). A review of feasibility studies by Totton et al. (22) evaluated three studies of sample size estimations. The most recent of these studies was by Teare et al. (23), who recommend 60 participants per arm for feasibility studies with binary outcomes. 60 participants per cohort will generate sufficient results for feasibility and acceptability to achieve the proposed outcomes.

This sample size will also provide sufficient data for analysis of the secondary outcomes. As these are concerned with the level of agreement between the two ultrasound modalities, we will use Bland-Altman limits of agreement. Studies using this method rarely include sample size calculations, with an average sample size of 65.(24) The overall assessment of the devices from the combined three groups will involve a total sample of 180 paired scans.

Diabetes: The Diabetes antenatal clinic at LWH runs once a week on Tuesdays and sees between 20-40 patients per week. During a six-month period, this will equate to around 750 patients.

SGA: The Growth clinics at LWH run twice a week on Mondays and Thursdays and see roughly six patients per clinic. During a six-month period, this will equate to around 300 patients.

RFM: Patients present with RFM regularly to MAU at LWH. Around four patients per day will present. In a six-month period, this will equate to around 700 patients. The PI will aim to recruit from this clinical area weekly on Fridays.

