#### **POCUS versus SUM**

#### 5.2. Outcome

The primary outcomes will be the acceptability and feasibility of point-of-care ultrasound to patients. This will be assessed as:

- 1) The number of patients approached who agree to participate (objective 1)
- 2) The response rate to the questionnaire (objectives 2 and 3)
- 3) The number of patients willing to undergo POCUS scans in the future as determined by the questionnaire responses (objective 2)
- 4) The number of unblinding episodes that occur (objective 4)

The exploratory outcomes will investigate the reliability and validity of the point-of-care ultrasound device. This will be assessed as:

- 1) For categorical data, Kappa coefficients demonstrating 90% agreement or greater (objectives 1 and 2)
- 2) For numerical data, ICC 0.9 or greater (objectives 1 and 2)
- 3) For continuous data (fetal biometric measurements), high level of agreement with Bland Altman, defined as ≥95% of the differences between the two measurement methods fall within the clinically acceptable range of ±3 to ±7 mm, depending on gestational age (objectives 1 and 2)
- 4) The difference in the mean time taken to perform each type of scan (POCUS and SUM) (objective 3)
- 5) The number of patients in whom fetal assessment could not be performed (objective 2)
- 6) Data from the feasibility study will inform the sample size calculation for the full randomized controlled trial by providing estimates of outcome variability, effect size, and recruitment parameters necessary for a power analysis (objective 4)

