### 10.2 Data Analysis

### Data analysis and statistical analysis plan

Data arising from the questionnaires will be analysed in Microsoft Excel and will be reported using descriptive summary statistics, mean, medians, and counts (i.e. "54% of participants were satisfied with the POCUS scan").

Acceptability will be assessed using descriptive summary statistics, mean, medians, counts, and corresponding measures of variability.

Data will be analysed using SPSS (Statistical Package for the Social Sciences, IBM, Armonk NY).

The statistical methods have been chosen in collaboration with and at the advice of a University of Liverpool statistician ([name]) to ascertain agreement between the two methods of scanning (POCUS and SUM), and to enable appropriate statistical analysis of the proposed sample. Within each group we will use interclass correlation coefficients (ICC) and Spearman correlation coefficients (SCC) to check how closely the two methods agree by looking at the agreement between the paired measurements. Intraclass correlation coefficients measure how similar the measurements from the two methods are, indicating reliability or consistency for continuous variables. As the ICC approaches 1 (0.9 or greater), the greater the level of agreement. For this study, an ICC of 0.9 or greater will be considered a high level of agreement and indicate

increased reliability of the Vscan device.

To assess for difference in the scan duration, the mean scan time, median and interquartile ranges will be used. We will examine for correlation between the continuous variables of BMI and scan time with both POCUS and standard ultrasound. Calculation of a correlation coefficient will be performed with Spearman's correlation test.

Kappa coefficients measure agreement for categorical outcomes, such as assessments of fetal presentation or amniotic fluid levels. Values  $\leq 0$  indicate no agreement, 0.01–0.20 as none to slight, 0.21–0.40 as fair, 0.41–0.60 as moderate, 0.61–0.80 as substantial, and 0.81–1.00 as almost perfect agreement. These methods will be used to check for similarity within the methods (POCUS or SUM). This will ensure the measurements taken by the methods themselves are consistent.

Calculating the mean difference and 95% confidence intervals will provide estimate of any offset between two devices. Bland-Altman plots with limits of agreement will also provide a visual indication of the level of agreement between the two devices.

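### Section 10.1 calls the sample sufficient for the agreement outcomes without showing precision; with at most 60 pairs per cohort, the ICC mark of 0.9 cannot reliably sort values near it

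*Protocol*

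**What the plan says.** Section 10.1 (Sampling) is open about how the size was chosen: "As this is an exploratory study and no hypothesis testing is planned a formal sample size calculation has not been performed". It sets the cohorts ("We will aim to include 60 patients per cohort") and the totals ("There will be three cohorts, so the total number of patients will be 180, and the number of scans performed 360"). The 60 comes from a published recommendation for feasibility studies with binary outcomes.

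The section then extends this size to the agreement outcomes: "This sample size will also provide sufficient data for analysis of the secondary outcomes". Section 5.2 has no secondary outcomes; the agreement outcomes appear there as exploratory. Two supports follow. One is about practice in other studies: "Studies using this method rarely include sample size calculations, with an average sample size of 65". The other is the combined sample: "The overall assessment of the devices from the combined three groups will involve a total sample of 180 paired scans".

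Section 10.2 sets the level of the ICC analysis: "Within each group we will use interclass correlation coefficients (ICC) and Spearman correlation coefficients (SCC) to check how closely the two methods agree". Its later sentences on the mean difference and the Bland-Altman plots refer to the two devices and do not say whether they apply by cohort or to all pairs.

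Section 5.2 gives the marks: "For numerical data, ICC 0.9 or greater (objectives 1 and 2"; and, for biometry, at least 95% of differences inside a millimetre range that depends on gestation. Both are tied to exploratory objectives 1 and 2, and objective 2 is validity by risk group (SGA, diabetes, RFM). Neither mark is stated with a confidence limit.

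**The concern.** An average of sizes that were mostly not calculated describes habit and says nothing about adequacy. The combined 180 cannot support an analysis that section 10.2 carries out on a third of that number. The recommendation behind the 60 is for binary feasibility outcomes, which is a different question from agreement.

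Objective 2 asks how the device performs in three risk groups. If each cohort's ICC is read as a pass or fail at 0.9, three cohorts with the same true agreement can easily receive different verdicts. A reader told that the data are sufficient could take such a contrast for a real effect of diabetes, SGA or RFM on the device.

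**Working it through.** **Inputs from the protocol.** 60 per cohort, three cohorts, two scans each (10.1); ICC mark 0.9 and 95%-in-range mark (5.2); ICC within each cohort (10.2). The 95% confidence level is stated in 10.2 for the mean difference and is assumed here for every interval.

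**Plan's own figures.** 3 × 60 = 180 patients and 2 × 180 = 360 scans. Both reproduce. The sufficiency statement gives no inputs, so there is nothing to reproduce.

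**Assumptions.** Independent pairs; for the ICC, normal data, a one-way model with two measurements and no systematic offset; all 60 pairs evaluable. Section 5.2 expects some assessments to be impossible but gives no rate, so 60 is an upper bound.

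**1. Precision of the ICC.** An observed ICC of r corresponds to F = (1 + r)/(1 − r); r = 0.90 gives F = 1.90/0.10 = 19. Divide and multiply F by the 97.5% points of the F distribution on (n − 1, n) and (n, n − 1) degrees of freedom, then convert back with (F − 1)/(F + 1).
- n = 60: 19/1.670 = 11.38 gives 10.38/12.38 = 0.838; 19 × 1.671 = 31.76 gives 30.76/32.76 = 0.939. CI 0.84 to 0.94.
- n = 180: 19/1.341 = 14.17 gives 0.868; 19 × 1.341 = 25.48 gives 0.924. CI 0.87 to 0.92.
- If 10 pairs are lost (assumed, n = 50): 0.83 to 0.94.

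**2. Chance that the observed ICC reaches 0.9.** This is P(F on (n − 1, n) df > 19/F0), with F0 = (1 + ρ)/(1 − ρ) for a true ICC of ρ.

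| True ICC | n = 60 | n = 180 |
|---|---|---|
| 0.85 | 4.9% | 0.2% |
| 0.87 | 14.3% | 3.2% |
| 0.90 | 50% | 50% |
| 0.92 | 81.5% | 94.1% |
| 0.95 | 99.7% | 100.0% |

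If all three cohorts truly have ICC 0.92, the chance that their verdicts disagree is 1 − 0.815³ − 0.185³ = 1 − 0.541 − 0.006, about 45%.

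**3. In-range mark, if it is applied by cohort.** 95% of 60 is 57, and 95% of 180 is 171. The exact binomial chances of passing are:

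| True share in range | 57 of 60 | 171 of 180 |
|---|---|---|
| 85% | 1.5% | 0.0% |
| 90% | 13.7% | 1.2% |
| 92% | 28.3% | 8.3% |
| 95% | 64.7% | 58.7% |
| 97% | 89.4% | 95.4% |
| 98% | 96.8% | 99.6% |

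The Clopper-Pearson 95% CI is 86.1% to 99.0% for 57/60 and 90.7% to 97.7% for 171/180. Even 60/60 has a two-sided lower limit of 0.025^(1/60) = 94.0%, so no cohort result can place that limit at 95%.

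**4. Limits of agreement.** The 95% CI half-width of each limit, in SDs of the differences, is 1.96 × √(1/n + 1.96²/(2(n − 1))).
- n = 60: 1.96 × √(0.01667 + 0.03256) = 0.43.
- n = 180: 1.96 × √(0.00556 + 0.01073) = 0.25.

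**The case against.** The best reply is that these outcomes are exploratory, no test is planned, and section 10.1 openly says that no formal calculation was made. No comparison of agreement between cohorts is specified, and no decision on a later trial depends on a cohort passing. This stands, and it means that no power calculation is owed. It does not justify stating that the data are sufficient, or setting numerical marks without saying how precisely they can be read.

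A reader might infer that 60 pairs cannot distinguish adequate from inadequate agreement at all. The figures do not support that: a true ICC of 0.85 passes 4.9% of the time and 0.95 passes 99.7%; a true in-range share of 85% passes 1.5% and 98% passes 97%. Some blurring at the mark belongs to any point-estimate threshold. At a true ICC of 0.90 the pass rate is 50% at both sizes, and at a true share of 95% it is lower at 180 (59%) than at 60 (65%).

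A reader might also infer that the protocol judges Bland-Altman agreement by cohort, or that it has no combined analysis. Neither follows. The within-group wording in 10.2 covers ICC and Spearman only, and 10.1 mentions a combined assessment of 180 pairs. A per-cohort use of the in-range mark can be drawn only from its link to objective 2, so the 57/60 figures are conditional. The level of each analysis may also be settled in an SAP not at hand.

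Nor does it matter that 60 is below 65: the half-width of a limit of agreement is 0.43 SD at 60 and 0.42 SD at 65.

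**Conclusion.** The concern holds in a limited form. The sufficiency statement in 10.1 is unsupported for the within-cohort ICC analysis in 10.2, because neither an average from other studies nor the combined N shows the precision of a cohort estimate. With at most 60 pairs, a point-estimate mark does not reliably sort true ICCs of about 0.87 to 0.92 (0.87 passes 14%, 0.92 fails 18.5%). If the in-range mark is also used by cohort, the same is true of shares of about 90% to 97% (90% passes 14%, 97% fails 11%). Passing a mark on the point estimate therefore does not show that a cohort meets the standard, and different verdicts in two cohorts do not show that they differ. The primary feasibility outcomes are untouched.

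The results rest on the assumptions listed with the calculation; lost pairs would widen the intervals.

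**What to change.** In 10.1, replace the sufficiency sentence and the argument from the average of 65 with the precision delivered:
- observed ICC 0.90: 95% CI 0.84 to 0.94 at n = 60, and 0.87 to 0.92 at n = 180;
- 95% of differences in range: 86% to 99% for 57/60, and 91% to 98% for 171/180;
- limits of agreement: ±0.43 SD at n = 60, and ±0.25 SD at n = 180.

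In 10.2, report each cohort's ICC and in-range share with a 95% CI, and state that no cohort will be declared reliable, or different from another, on the point estimate alone. Specify the combined 180-pair assessment that 10.1 already mentions, alongside the cohort estimates. It should not replace them: judging the marks on pooled data only would weaken objective 2 and could hide one poorly performing cohort.

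The cost is protocol wording and one further analysis of data already being collected, with no extra patients. The drawback is that the study can no longer offer a firm reliability verdict for each cohort.

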#### Data collection

Data will be obtained from patient records and the scans performed and recorded via a CRF. We will utilize a secure, web-based data entry system accessible at https://redcap.liverpool.ac.uk/ for recording the data. It is the responsibility of the PI to ensure the accuracy of all data entered and documented in the CRFs. Review of the data may occur at the discretion of the other members of the trial steering group.

Data will be collected from participant questionnaires undertaken on paper and transcribed into REDCap. Each response will be coded with the participant's Trial ID number.

### 10.2 Data Analysis

### Data analysis and statistical analysis plan

Data arising from the questionnaires will be analysed in Microsoft Excel and will be reported using descriptive summary statistics, mean, medians, and counts (i.e. "54% of participants were satisfied with the POCUS scan").

Acceptability will be assessed using descriptive summary statistics, mean, medians, counts, and corresponding measures of variability.

Data will be analysed using SPSS (Statistical Package for the Social Sciences, IBM, Armonk NY).

The statistical methods have been chosen in collaboration with and at the advice of a University of Liverpool statistician ([name]) to ascertain agreement between the two methods of scanning (POCUS and SUM), and to enable appropriate statistical analysis of the proposed sample. Within each group we will use interclass correlation coefficients (ICC) and Spearman correlation coefficients (SCC) to check how closely the two methods agree by looking at the agreement between the paired measurements. Intraclass correlation coefficients measure how similar the measurements from the two methods are, indicating reliability or consistency for continuous variables. As the ICC approaches 1 (0.9 or greater), the greater the level of agreement. For this study, an ICC of 0.9 or greater will be considered a high level of agreement and indicate

increased reliability of the Vscan device.

To assess for difference in the scan duration, the mean scan time, median and interquartile ranges will be used. We will examine for correlation between the continuous variables of BMI and scan time with both POCUS and standard ultrasound. Calculation of a correlation coefficient will be performed with Spearman's correlation test.

Kappa coefficients measure agreement for categorical outcomes, such as assessments of fetal presentation or amniotic fluid levels. Values  $\leq 0$  indicate no agreement, 0.01–0.20 as none to slight, 0.21–0.40 as fair, 0.41–0.60 as moderate, 0.61–0.80 as substantial, and 0.81–1.00 as almost perfect agreement. These methods will be used to check for similarity within the methods (POCUS or SUM). This will ensure the measurements taken by the methods themselves are consistent.

Calculating the mean difference and 95% confidence intervals will provide estimate of any offset between two devices. Bland-Altman plots with limits of agreement will also provide a visual indication of the level of agreement between the two devices.

These methods evaluate both quantitative and qualitative agreement across different types of data (continuous and categorical) and aim to verify if POCUS aligns with SUM in measuring fetal parameters accurately.

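### The ICC is described as a consistency measure, but its 0.9 mark is read as agreement and no ICC form is named; a consistency ICC cannot see a constant offset between the devices

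*Protocol*

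**What the plan says.** Protocol section 10.2 applies the ICC and Spearman's coefficient within each group "to check how closely the two methods agree by looking at the agreement between the paired measurements". It describes the coefficient so: "Intraclass correlation coefficients measure how similar the measurements from the two methods are, indicating reliability or consistency for continuous variables". Shortly afterwards it sets the mark: "For this study, an ICC of 0.9 or greater will be considered a high level of agreement and indicate" increased reliability of the hand-held device. Section 5.2 repeats this as exploratory outcome 2: "For numerical data, ICC 0.9 or greater (objectives 1 and 2". Neither section says whether the ICC is of the consistency or the absolute-agreement form, and neither gives the model.

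Two other elements bear on a device offset:

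- Section 10.2: "Calculating the mean difference and 95% confidence intervals will provide estimate of any offset between two devices". Bland-Altman plots with limits of agreement accompany this. No acceptance limit is attached to the mean difference.
- Section 5.2, exploratory outcome 3, for fetal biometry: at least 95% of "the differences between the two measurement methods fall within the clinically acceptable range of ±3 to ±7 mm, depending on gestational age".

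Appendix 1 (section 14.1) records HC, AC and FL in millimetres and EFW in grams, on both devices.

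**The concern.** For two methods measured on the same fetuses, consistency and absolute agreement are different coefficients. The consistency form removes the mean difference between methods before it is computed; the absolute-agreement form keeps that difference as error. Only the second supports reading 0.9 as agreement between POCUS and SUM. The one descriptor that section 10.2 offers points to the first. Spearman's coefficient, its companion, is also blind to a constant offset.

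If the consistency form were run, a device that reads short or long by a fixed amount could meet outcome 2 and be reported as agreeing well with standard ultrasound. If the form were chosen after the data were seen, the more favourable coefficient could be the one reported.

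**Working it through.** **The plan's own figures.** Section 10.1: "We will aim to include 60 patients per cohort". Three cohorts give 3 × 60 = 180 patients, and two scans each give 360 scans, as stated. The 0.9 mark is a fixed threshold, so there is nothing to reproduce for it.

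**Inputs.** The pairs per cohort (60), the mark (0.9) and the range (±3 to ±7 mm) come from the protocol. It gives no SD, error or expected offset; section 10.1 says "no hypothesis testing is planned a formal sample size calculation has not been performed". The between-fetus SD (sb), the error SD per device (sw) and the constant offset (d) below are therefore assumptions.

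**Formulas, two methods.**

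- Consistency ICC = sb² / (sb² + sw²)
- Absolute-agreement ICC = sb² / (sb² + sw² + d²/2)
- Share of differences inside ±L: from a Normal distribution with mean d and SD sw√2

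**Worked example, FL** (sb 7, sw 1.5, d 4 mm). Consistency: 49 / (49 + 2.25) = 0.956. Absolute agreement: 49 / (49 + 2.25 + 8) = 0.827.

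**Scenarios.** The chance of reaching 0.9 comes from 4,000 simulated samples of 60 pairs, using the two-way ANOVA estimators.

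| Measure (sb, sw, d) | Consistency | Absolute agreement | Chance of ≥0.9, consistency v absolute | Inside ±7 mm |
|---|---|---|---|---|
| FL (7, 1.5, 4 mm) | 0.96 | 0.83 | 100% v 0.2% | 92% |
| AC (30, 5, 15 mm) | 0.97 | 0.87 | 100% v 6% | 13% |
| AC, gestational spread removed (12, 2.5, 5 mm) | 0.96 | 0.88 | 100% v 23% | 71% |
| EFW (600, 100, 250 g) | 0.97 | 0.90 (0.897) | 100% v 43% | not applicable |
| EFW (600, 100, 300 g) | 0.97 | 0.87 | 100% v 5% | not applicable |

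For EFW, absolute agreement equals 0.9 when d = √[2 × (360,000/0.9 − 360,000 − 10,000)] = √60,000, about 245 g. The 250 g row is therefore borderline.

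**Would outcome 3 catch the offset?** In the millimetre rows, yes. Even at the widest limit, ±7 mm, each falls short of 95%, and at ±3 mm the FL row drops to 32%. In the AC row with error SD 5 mm this is not due to offset alone: with no offset at all, only 68% of differences lie inside ±7 mm.

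**Is naming the form enough?** No. With sw = 2 mm, the largest offset at which absolute agreement still reaches 0.9 is √[2 × (sb²/0.9 − sb² − sw²)]:

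- sb 10 mm: √14.2 = 3.8 mm
- sb 20 mm: √80.9 = 9.0 mm
- sb 30 mm: √192 = 13.9 mm

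At sb 20 and sw 2 mm, a 7 mm offset gives 400 / (400 + 4 + 24.5) = 0.933, and 97% of samples pass. A 10 mm offset gives 400 / 454 = 0.881, and 14% pass. The consistency form stays at 400 / 404 = 0.990 and passes in every sample at both offsets.

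**The case against.** The strongest reply is that the plan does not overlook an offset. It estimates the offset directly, and outcome 3 sets a pass mark on raw differences that each millimetre example above fails whichever ICC is used. This stands. A reader might infer that a biased device would be declared acceptable because nothing could overturn the ICC result. For HC, AC and FL the documents do not support that. Nothing makes the ICC decisive over the other measures, although no rule says what follows if outcomes 2 and 3 disagree.

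Second, section 10.2 repeatedly gives agreement as its purpose, so the word consistency may be a loose gloss on ICCs in general. This also stands in part. A reader might infer that the plan has chosen the consistency form; it has not, and is only ambiguous.

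Third, the ICC form is often left to a separate SAP. Silence alone would not be a point. Here, however, the stated description conflicts with the stated reading of a fixed mark, in a subsection whose own title includes the statistical analysis plan.

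Fourth, section 6 builds EFW from HC, AC and FL, so a systematic EFW offset would have to arise in measurements that outcome 3 tests. This is fair and narrows the EFW gap. It does not close it: the protocol sets no acceptance limit in grams and does not translate the millimetre range into one.

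**Conclusion.** The point holds as a wording defect with a real but limited consequence. The description of the ICC does not match the conclusion drawn from it, and the form can decide whether 0.9 is reached (0.96 v 0.83 in the FL example). For HC, AC and FL, the likely result is an ICC wrongly labelled as agreement that may contradict outcome 3; an undetected bias is unlikely. For EFW, the ICC is the only numerical pass mark, so the label matters more there, subject to the dependence of EFW on the three biometric measures.

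All SDs, errors and offsets are assumed, and the gap between the two forms depends on the size of the offset relative to the between-fetus spread. The severity is minor: the outcome is exploratory, in a feasibility study with no hypothesis test, and no decision to progress is tied to the 0.9 mark.

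**What to change.** In section 5.2 (exploratory outcome 2) and section 10.2:

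- Name the coefficient as the two-way, absolute-agreement, single-measurement ICC, reported with its 95% CI, and apply the 0.9 mark to that coefficient only.
- In section 10.2, delete the words *or consistency*.
- State that conclusions about device offset rest on the mean difference and the limits of agreement, because an absolute-agreement ICC can also exceed 0.9 despite an offset when gestational spread is wide.

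The cost is a few sentences and one software option; no extra data are needed. The reported ICC may come out slightly lower.

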#### 3. RATIONALE FOR CURRENT STUDY

Increasing demand for ultrasound-based fetal growth surveillance is driven by the growing body of evidence implicating fetal growth restriction (FGR) and small for gestational age (SGA) as common causes of stillbirth, and a significant policy-based push toward reducing stillbirth rates at a national scale.

Patients at higher risk of FGR are identified following a risk assessment based on maternal characteristics and previous pregnancy outcomes, and are invited to undergo ultrasound assessment of fetal growth at regular intervals throughout the pregnancy (usually three to four weeks apart)(15). A cohort of these patients have risk factors that can make ultrasound assessment more challenging, including increased maternal body mass index (BMI) and diabetes leading to excess of amniotic fluid. Around one in 20 women who give birth in the UK have diabetes in pregnancy, either pre-existing or developed during the pregnancy. (16) Patients with diabetes and diagnosed SGA fetuses are required to attend more frequent scan appointments to ensure the fetal growth and wellbeing remains satisfactory (every two weeks or more if FGR is suspected). (17) Point-of-care devices are attractive to NHS services as they are more affordable than standard ultrasound machines, however it is unclear at present whether this is acceptable and feasible to deliver with training and image quality.

Patients presenting to the Maternity Assessment Unit (MAU) at or after 26 weeks of gestation with concerns regarding reduced fetal movements (RFM) in pregnancy represent a group with evolving risk for FGR. These patients are routinely offered a computerised CTG (cCTG) and an ultrasound scan assessment of fetal wellbeing comprising biometry, amniotic fluid volume assessment, and umbilical artery doppler studies. In our hospital, patients presenting with RFM at 39 weeks of gestation or greater are offered delivery via induction of labour or caesarean section and will only undergo ultrasound assessment in the event they decline delivery. As such, patients at 39 weeks or greater presenting with RFM will not be approached for this study.

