# **Exploratory Objectives:**

- 1) To evaluate the intraclass correlation (reliability) of hand-held POCUS for the assessment of second and third trimester fetal biometry
- 2) To assess the validity of hand-held POCUS in patients with different antenatal risk factors (SGA, Diabetes, and RFM)
- 3) To examine the efficiency of hand-held POCUS for second and third trimester assessment of fetal biometry
- 4) To determine the minimum sufficient sample size to detect a difference in measurements taken with

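### For AC and HC, an ICC of 0.9 on raw millimetre values can be labelled high agreement while the protocol's own millimetre limit is missed; Spearman correlation does not measure agreement at all

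*Protocol*

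**What the plan says.** Three places in the protocol bear on this.

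- **Section 5.1, exploratory objective 1** identifies reliability with the ICC, over a wide gestational range: "To evaluate the intraclass correlation (reliability) of hand-held POCUS for the assessment of second and third trimester fetal biometry".
- **Section 5.2** lists two criteria for exploratory objectives 1 and 2. One is an ICC of at least 0.9 for numerical data. The other, for fetal biometry, is that "≥95% of the differences between the two measurement methods fall within the clinically acceptable range of ±3 to ±7 mm, depending on gestational age". It does not say which decides if they differ.
- **Section 10.2** says: "Within each group we will use interclass correlation coefficients (ICC) and Spearman correlation coefficients (SCC) to check how closely the two methods agree". It then says: "For this study, an ICC of 0.9 or greater will be considered a high level of agreement", and treats such a value as a sign that the device is more reliable. It also plans the mean difference with a 95% confidence interval, and Bland-Altman plots, which it describes as a visual indication; the millimetre limit is not repeated there.

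On gestation, section 3 describes reduced-fetal-movement (RFM) patients presenting "at or after 26 weeks of gestation" and says that those at 39 weeks or more will not be approached. Section 8.1 sets no gestational window for the diabetes or SGA cohorts. Gestation at the scan is collected (section 6 and Appendix 1), but no adjustment of the ICC or Spearman coefficient for it is stated.

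**The concern.** The ICC is the between-patient variance divided by the total variance. When HC, AC and FL in millimetres are pooled over many weeks of pregnancy, much of the between-patient variance is fetal growth, which says nothing about how well two devices agree on one fetus. The same device error therefore earns a higher ICC in a cohort with a wider spread of gestation. A fixed threshold of 0.9 has no fixed meaning in millimetres, yet section 10.2 attaches a verdict to it.

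Spearman correlation measures whether the two devices rank fetuses in the same order. Adding a constant to every POCUS reading leaves it unchanged, so it cannot show how closely the devices agree.

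At stake is the reliability claim carried forward. Section 3 says the study is to guide later studies and their statistical methods, and feasibility objective 3 asks whether the outcome measures are suitable for assessing reliability. A favourable ICC could be quoted on data where the millimetre criterion fails.

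**Working it through.** **Inputs from the protocol.** ICC threshold 0.9 (sections 5.2 and 10.2); limits of ±3 to ±7 mm for at least 95% of differences (5.2); 60 patients per cohort (10.1); RFM gestation 26 to under 39 weeks (3). The protocol gives no derivation of 0.9, so there is no figure to reproduce. It gives no biometric SDs, so all SDs and growth slopes below are assumptions.

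**Step 1: the ICC threshold in millimetres.** Assume equal error variances and no bias. Let sb be the between-patient SD and se the error SD of each device.

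- ICC = sb² / (sb² + se²) = 0.9 gives se = sb/3.
- SD of the paired differences = √2 × sb/3 = 0.471 sb.
- 95% limits of agreement = ±1.96 × 0.471 sb = ±0.924 sb.

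**Step 2: where the two criteria match.** 7/0.924 = 7.6 mm and 3/0.924 = 3.2 mm. Above these between-patient SDs, an ICC of 0.9 is laxer than the ±7 mm and ±3 mm limits respectively.

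**Step 3: size at assumed SDs for HC or AC.** The last column uses an SD of differences of 7/1.96 = 3.57 mm, so se² = 3.57²/2 = 6.38.

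| sb (assumed) | SD of differences at ICC 0.9 | Limits of agreement | Within ±7 mm | ICC when 95% lie within ±7 mm |
|---|---|---|---|---|
| 20 mm | 9.4 mm | ±18.5 mm | 54% | 400/406.4 = 0.984 |
| 30 mm | 14.1 mm | ±27.7 mm | 38% | 900/906.4 = 0.993 |

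**Step 4: dependence on the gestation window.** Take gestation as uniform over the window, with total SD = √[(slope × window/√12)² + (SD at fixed gestation)²]. In terms of total SD, the limits at ICC 0.9 are ±1.96 × √0.2 = ±0.877 × total SD. Assumed slopes (mm/week): AC 8–11, HC 5–9, FL 1.8–2.4. Assumed SDs at fixed gestation (mm): AC 10–18, HC 8–12, FL 2.2–3.5. Example, AC at the low end over 26–39 weeks: √[(8 × 13/3.464)² + 10²] = 31.6 mm, and 0.877 × 31.6 = 27.7 mm.

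| Window | AC limits (multiple of 7 mm) | HC limits (multiple of 7 mm) | FL limits (multiple of 7 mm) |
|---|---|---|---|
| 26–39 weeks | ±28 to 40 (4.0–5.6) | ±18 to 31 (2.6–4.5) | ±6 to 8.5 (0.9–1.2) |
| 28–36 weeks | ±18 to 27 (2.6–3.9) | ±12 to 21 (1.8–3.0) | ±4 to 6 (0.6–0.8) |
| 32–36 weeks | ±12 to 19 (1.7–2.8) | ±9 to 14 (1.2–2.0) | ±3 to 4 (0.4–0.6) |

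Against ±3 mm, FL over 26–39 weeks is 2.1–2.8 times the limit.

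**Step 5: simulation** (n = 60, 3,000 runs, mid-range assumptions, absolute-agreement ICC). Over 26–39 weeks with true limits of ±21 mm, about 49% of differences lie within ±7 mm. The ICC reached 0.9 in 100% of runs for AC and 96% for HC; the 95%-within-7-mm criterion was met in none. For FL the mismatch can reverse: over 28–36 weeks with true limits of ±7 mm, the ICC reached 0.9 in only 0.8% of runs.

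**Step 6: constant offset.** AC over 26–39 weeks, error SD 2.5 mm per device, POCUS reading 10 mm high throughout: Spearman 0.996, consistency ICC 0.996, absolute-agreement ICC 0.963, with 20% of differences within ±7 mm.

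**The case against.** The best defence is that the safeguard is already in the plan. Exploratory outcome 3 in section 5.2 is a millimetre criterion that does not depend on between-patient spread and varies with gestation. Section 10.1 names Bland-Altman limits as the method for the agreement outcomes. The mean difference in section 10.2 would reveal a constant offset. The form of the ICC and any regression on gestation are commonly left to a statistical analysis plan, which is not at hand. The outcomes are exploratory, with no hypothesis test and no progression rule tied to the ICC.

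Most of this stands, and it rules out several stronger readings that a reader might infer:

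- *That the ICC will pass whatever the device error.* It will not. At a between-patient SD of 20 mm, an SD of differences of 15 mm gives 400/(400 + 112.5) = 0.78.
- *That the two criteria are incompatible.* At 20 to 30 mm the millimetre limit is simply the stricter one, and a device meeting ±7 mm would also pass 0.9.
- *That a failing device would go unnoticed.* The Bland-Altman criterion and the mean difference would show it.
- *That every measurement is affected several-fold.* This does not hold for FL against ±7 mm, and for AC and HC it rests on assumed SDs and a wide gestation window.

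The unstated ICC form is not a fault in itself. What survives is text that the protocol does contain: a verdict attached to a raw ICC of 0.9, Spearman named as a check of agreement, and two criteria for the same objectives with no statement of which decides.

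**Conclusion.** The point holds in limited form and should be fixed before analysis; it does not threaten the study. An ICC of 0.9 on raw millimetre values is laxer than the protocol's limit whenever the between-patient SD exceeds about 7.6 mm (for ±7 mm) or 3.2 mm (for ±3 mm). That result needs only equal error variances and no bias.

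The size rests on SDs the documents do not give. At 20 to 30 mm for HC or AC, the limits allowed are 2.6 to 4.0 times ±7 mm. The excess shrinks to 1.2–2.8 times in a 32–36 week window and is about 1 for FL over 26–39 weeks. The misuse of Spearman needs no numerical assumption.

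The primary feasibility and acceptability outcomes are untouched. The harm is a possible report of high agreement next to a failed millimetre criterion, with no stated way to resolve the two.

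**What to change.** In sections 5.2 and 10.2:

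1. State that the Bland-Altman millimetre criterion decides agreement for HC, AC and FL, and repeat or cross-refer to it in 10.2.
2. Remove ICC of at least 0.9 as a stand-alone sign of high agreement. Report the ICC descriptively, in absolute-agreement form, on gestation-adjusted values (z-scores, or residuals from a regression on gestation). Choosing the absolute-agreement form without adjusting is not enough, as step 6 shows.
3. Remove Spearman as a measure of agreement between devices; keep it for BMI against scan time.

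The cost is wording plus one regression on a variable already collected, with no new data and no change in sample size. The downside is that the reported ICC will look less favourable and will be harder to set beside unadjusted ICCs from other studies.
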